5.6.1.2. Rescue Medication

Subjects requiring rescue medication will be given appropriate medication in accordance with site (local) or national treatment guidelines for *P. vivax* malaria or; e.g., *P. falciparum* malaria, whichever is applicable. Subjects offered rescue medication should be followed up for safety assessment until resolution of the malaria infection.

Details of rescue medication including reason for the rescue medication offered (e.g. withdrawal from study, treatment failure) should be recorded in the eCRF.

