Pharmacokinetic Assessments																
PK/PD Sampling ^u		X	X		X		X		X	X					X	
Investigational Product																
Dispense Open Label Chloroquine	X	X	X													
Dispense Blinded Study Medication	X ^v	X ^v														
Treatment Compliance Int. - Invest.	X	X	X	X	X	X	X									
IVRS Registration	X															

- a All subjects must remain hospitalized for Days 1 through 3.
- b Subjects who relapse will continue to be monitored for safety and efficacy at all scheduled visits through day 180. Relapse is defined by a positive blood smear with or without vivax symptoms.
- c If subjects withdraw from blinded study medication, all scheduled follow-up visits should be performed to conduct safety assessments up to and including Day 180.
- d Visit Day 1 includes all screening procedures and the first day of treatment with study medication.
- e Includes medical, disease and therapy histories.
- f Blood smears are to be taken twice a day, 6-12 hours apart for the first 3 days, or until 2 consecutive negative thick blood smears are obtained.
- g Vital signs include height and weight (screening only), blood pressure, temperature, heart rate and respiratory rate. Vital signs are to be performed twice a day on Days 1 through 3, at least 4 hours apart, and immediately prior to PK measurements.
- h ECGs are to be performed at screening (in triplicate), 12 hours after the first dose of blinded study medication, and on Day 29.
- i Adverse events are recorded from the time of the first dose of study medication.
- j Serious adverse events are recorded from the time of consent in order to fulfil international regulatory requirements.
- k G6PD phenotyping to be performed by quantitative spectrophotometric analysis. One or more G6PD rapid point of care tests may be performed at baseline (Day 1) only.
- l Only if Day 90 ophthalmological exam shows abnormalities.
- m Hematology includes hemoglobin, hematocrit, red blood cell/white blood cell/platelet counts, mean cell volume, white blood cell differential and reticulocyte count.

- n Hematology and clinical chemistry on Day 3 must be reviewed prior to discharge from the hospital.
- o Clinical Chemistry includes CPK, BUN, serum creatinine, total and indirect bilirubin and liver clinical chemistry.
- p Mid-stream urine will be analyzed for protein, glucose, ketones, bilirubin, blood, nitrites, urobilinogen and leukocyte esterase by dipstick method.

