- If a subject has a relapse outcome and a censored outcome, they will be considered to be a relapse, even if the time point of the relapse is later than the time point of censoring. For example, a subject who took a medication with anti-malarial activity at Study Day 32, but remained parasite-free after initial clearance until Study Day 68 will be treated as a relapse at Study Day 68.

Relapse free efficacy and Time to Relapse

Flow chart of algorithm:

Four months

[figure not shown]
- A subject will be considered to have demonstrated relapse-free efficacy at 4 months for the purposes of the analysis if **all** of the following are true (also described in the flowchart below)::
 - Subject had a non-zero *P. vivax* asexual parasite count at baseline. Subjects with no asexual *P. vivax* parasites at this time point will be censored with time to relapse = 0 days.
 - Subject demonstrated initial clearance of *P. vivax* parasitaemia. This is defined as two negative asexual *P. vivax* parasite counts, with at least 6 hours between the counts, and no positive counts in the interval. Subjects who do not meet this criteria will be classified as relapses, with time to relapse = 0 days.
 - Subject has no positive asexual *P. vivax* parasite count at any assessment prior to or on Study Day 130 following initial parasite clearance. Subjects who do have a positive count will be classified as relapses, with time to relapse = (date of first positive count) – (date of Study Day 1) days.
 - Subject did not take a concomitant medication with anti-malarial activity at any point between Study Day 1 and their first parasite assessment after Study Day 109 (up to and including Study Day 130). A list of all concomitant medications will be reviewed by a GSK clinician prior to unblinding the study, and classified accordingly. Subjects who did take a drug with anti-malarial activity but never had a positive asexual *P. vivax* parasite count after initial clearance will be censored, with time to relapse censored at (date of last negative parasite assessment prior to concomitant medication start) – (date of Study Day 1). If a

Relapse free efficacy and Time to Relapse

subject has not had a negative assessment prior to the concomitant medication start date, they will be censored at 0.

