- Subject is parasite-free at 4 months. This is defined as a negative asexual *P. vivax* parasite count at the first parasite assessment performed after Study Day 109 (up to and including Study Day 130).
- Subjects who do not have a positive asexual *P. vivax* parasite count following initial clearance but where the final parasite count occurred on or before Study Day 109 will not have been classified by the preceding rules. These subjects will be considered to be censored, with time to relapse censored at (Date of final parasite assessment) – (date of Study Day 1).
- If a subject has a relapse outcome and a censored outcome, they will be considered to be a relapse, even if the time point of the relapse is later than the time point of censoring. For example, a subject who took a medication with anti-malarial activity at Study Day 32, but remained parasite-free after initial clearance until Study Day 68 will be treated as a relapse at Study Day 68.

Flow chart of algorithm:

Relapse free efficacy at 6 months missing=failure definition

- In addition to those with a positive asexual *P. vivax* parasite count at any assessment prior to or on Study Day 201, the following subjects will also be defined to have relapsed:
 - Subject did not demonstrate initial clearance of *P. vivax* parasitaemia (i.e. did not have

Relapse free efficacy and Time to Relapse
 
two negative asexual P. vivax parasite counts, with at least 6 hours between the counts, and no positive counts in the interval)
 
 ○ Subject took a concomitant medication with anti-malarial activity at any point between Study Day 1 and their last parasite assessment. A list of all concomitant medications will be reviewed by a GSK clinician prior to unblinding the study, and classified accordingly. ○ Subject does not have a parasite assessment between Study Day 166 and 201. 
 ● Subjects with a zero P. vivax asexual parasite count at baseline will be excluded from the analysis.

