
Relapse free efficacy at 6 months missing on or after Day 29=failure definition
 
 ● In addition to those with a positive asexual P. vivax parasite count at any assessment prior to or on Study Day 201, the following subjects will also be defined to have relapsed: 
 ● Subject did not demonstrate initial clearance of P. vivax parasitaemia (i.e. did not have two negative asexual P. vivax parasite counts, with at least 6 hours between the counts, and no positive counts in the interval) ● Subject took a concomitant medication with anti-malarial activity at any point between Study Day 1 and their last parasite assessment. A list of all concomitant medications will be reviewed by a GSK clinician prior to unblinding the study, and classified accordingly. ● Subject with a missing parasite assessment on or after the Day 29 assessment ● Subjects with a zero P. vivax asexual parasite count at baseline will be excluded from the analysis.

Relapse free efficacy at 4 months missing=failure definition
 
 ● In addition to those with a positive asexual P. vivax parasite count at any assessment prior to or on Study Day 130, the following subjects will also be defined to have relapsed: 
 ○ Subject did not demonstrate initial clearance of P. vivax parasitaemia (i.e. did not have two negative asexual P. vivax parasite counts, with at least 6 hours between the counts, and no positive counts in the interval) ○ Subject took a concomitant medication with anti-malarial activity at any point between Study Day 1 and their last parasite assessment. A list of all concomitant medications will be reviewed by a GSK clinician prior to unblinding the study, and classified accordingly. ○ Subject does not have a parasite assessment between Study Day 110 and 130. ● Subjects with a zero P. vivax asexual parasite count at baseline will be excluded from the analysis.

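### The 4-month missing=failure rule counts anti-malarials taken after the 4-month assessment, so some subjects confirmed relapse-free at 4 months become failures in Table 2.16

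*Supplement*

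**What the plan says.** All RAP references are to Amendment 1 (21-FEB-2017), section 13.6.4.

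**4-month missing=failure definition.** Three of its criteria carry a time limit:
- Positive smears: "In addition to those with a positive asexual P. vivax parasite count at any assessment prior to or on Study Day 130".
- Missing assessment: "Subject does not have a parasite assessment between Study Day 110 and 130".
- Anti-malarials: "Subject took a concomitant medication with anti-malarial activity at any point between Study Day 1 and their last parasite assessment".

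The first two end at Day 130. The third ends at the last smear, whenever that is. The 6-month missing=failure definition has the same anti-malarial wording, and there it matches its smear criterion: "Subject does not have a parasite assessment between Study Day 166 and 201".

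**Main 4-month definition.** The anti-malarial look-back runs "between Study Day 1 and their first parasite assessment after Study Day 109 (up to and including Study Day 130". A negative smear in the same window confirms relapse-free status. Censoring for incomplete follow-up is given to subjects "where the final parasite count occurred on or before Study Day 109 will not have been classified by the preceding rules".

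**Follow-up and rescue (protocol Amendment 5).** Section 5.6.1.2: "Subjects requiring rescue medication will be given appropriate medication in accordance with site (local) or national treatment guidelines". Time and Events table, footnote b: "Subjects who relapse will continue to be monitored for safety and efficacy at all scheduled visits through day 180". RAP 13.6.2 treats any drug started on or after the first study dose as concomitant and does not exempt rescue.

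**Table 2.16 footnote (RAP 13.14.4).** It lists anti-malarial use as a reason for failure and gives no time limit.

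**The concern.** Within one definition, the smear criteria describe status at 4 months while the drug criterion describes status at the end of follow-up. A relapse is normally followed by rescue and then by further scheduled smears, so rescue for a relapse after Day 130 will often precede the last smear and trigger the bullet. The subject then fails at 4 months with no data missing, which is not what a missing=failure analysis is meant to test.

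The effect is wider than relapse. *P. falciparum* treatment, or any other drug that the sponsor's clinician classes as active, taken after the 4-month smear and before the last one has the same result.

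At stake is the estimate in Table 2.16. Its failure rate moves towards the 6-month rate, and its odds ratio picks up events from after the time point it is labelled with.

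**Working it through.** The plan states no figure for this analysis, so there is none to reproduce. The check has three parts.

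**1. Rule applied to example subjects.** Smears are on protocol Days 1, 2, 3, 8, 15, 22, 29, 60, 90, 120, 150 and 180 (plus Day 140 where an unscheduled visit is assumed). The limited version ends the look-back at the first smear in Days 110–130.

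| Subject | As written | Limited |
|---|---|---|
| Relapse and rescue Day 150 | failure | relapse-free |
| Relapse and rescue Day 140 (unscheduled) | failure | relapse-free |
| No vivax relapse, falciparum treated Day 160 | failure | relapse-free |
| Relapse Day 180, rescue Day 181 | relapse-free | relapse-free |
| Relapse and rescue Day 90 | failure | failure |
| No relapse, no drug | relapse-free | relapse-free |

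The fourth row shows the limit of the problem: rescue begun after the last smear is not caught. Rescue on the same day as the last smear is ambiguous.

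**2. Share of subjects affected by late relapse.** The documents give no late-relapse rate, so a constant hazard and a relapse proportion r by Day 180 are assumed, with relapse dated by its first positive smear.

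h = −ln(1 − r)/180; relapse between days a and b = exp(−ah) − exp(−bh).

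| r | exp(−130h) | exp(−150h) | 1 − r | Days 130–150 | Days 130–180 |
|---|---|---|---|---|---|
| 20% | 0.851 | 0.830 | 0.800 | 2.1 pp | 5.1 pp |
| 30% | 0.773 | 0.743 | 0.700 | 3.0 pp | 7.3 pp |
| 40% | 0.691 | 0.653 | 0.600 | 3.8 pp | 9.1 pp |

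The Days 130–150 column assumes that every later relapse is found at the final smear and rescued afterwards. The Days 130–180 column assumes that every relapse is rescued before the last smear, so it is an upper bound. With r = 30%, true 4-month failure is 1 − 0.773 = 22.7%; the rule as written gives about 25.7% (22.7 + 3.0) to at most 30% (22.7 + 7.3). Anti-malarial use for reasons other than relapse would come on top.

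**3. Effect on the odds ratio.** The meta-analysis plan (section 3) reports 251 randomised 2:1, about 167 and 84. Assume true 4-month relapse-free rates equal in both arms, so the true odds ratio is 1.00.
- Late anti-malarial use of 5% in each arm adds about 8 and 4 failures (167 × 0.05 and 84 × 0.05) and leaves the odds ratio at 1.00.
- With 5% on TQ and 10% on PQ and a true rate of 75%, the odds ratio is (0.70/0.30)/(0.65/0.35) = 1.26. Over true rates of 65–85% it is 1.23–1.33.
- With the late rates reversed, it is 0.75–0.81.

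**The gap in the main 4-month text.** Take a subject with no positive count up to Day 130, no smear in Days 110–130, no anti-malarial use, and a smear at Day 150 or 180. The subject is not relapse-free (no confirming smear), not a relapse (no positive by Day 130), and not censored (the final count is after Day 109).

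**The case against.** **The analysis is minor.** It is a supportive analysis of a secondary endpoint in a trial that tests no hypotheses on it. This stands. A reader might infer that the trial's main results are affected, but the documents do not support that. The primary haemolysis analysis, the main 4-month survival and logistic analyses (Tables 2.11, 2.12 and 2.14), all 6-month analyses and the 6-month meta-analysis do not use this rule. The Headline label on Table 2.16 marks a delivery batch that also contains demographics.

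**The unlimited drug criterion comes from the protocol.** Protocol 8.3.4.3 treats four and six months together and fails anyone who took a drug active against *P. vivax*, with no time limit. So it is not shown that the 6-month wording was copied by mistake. That does not justify the bullet: the same protocol sentence refers to a six-month result, and the RAP replaced it for 4 months with its own Day 110–130 window. Only the drug criterion ignores that window.

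**The rule is conservative by design.** Adding failures does not make a comparison of two active arms conservative. The odds ratio can move either way, or stay at 1.00 if late use is equal by arm.

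**The size is uncertain.** It is. Reading 5–9 points as the expected effect would be too strong, because rescue after the final smear is not caught and the constant hazard is an assumption.

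**The flowchart may close the second gap.** The RAP says that the 4-month rule is also given as a flowchart, which is not shown. The gap is therefore established for the text only. Such subjects do count as failures in missing=failure, and a missed Day 120 smear excludes them from per protocol.

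**Conclusion.** The concern holds in a limited form and should be fixed. As written, the 4-month missing=failure rule misclassifies any subject confirmed relapse-free in Days 110–130 who takes an anti-malarial after that smear and before the last one. Under a constant hazard with 20–40% relapse by Day 180, late relapse adds about 2–4 percentage points of failures if only relapses in Days 130–150 are caught, and 5–9 points at most. Bias in the odds ratio depends on late use differing by arm, on which the documents give no information.

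The unclassified subjects in the main 4-month text are a separate, smaller point. It does reach the main 4-month outputs, but only if the flowchart does not already resolve it.

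**What to change.** 1. In the 4-month missing=failure definition, count anti-malarial use only from Study Day 1 up to the subject's first smear in Study Days 110–130, or up to Study Day 130 if there is none.
2. Put the same limit in the Table 2.16 footnote. Otherwise the RAP would contradict itself.
3. In the main 4-month definition, state that a subject with no positive count up to Study Day 130 and no smear in Study Days 110–130 is censored at the last smear on or before Study Day 109. Check that the flowchart agrees.

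The cost is two bullets, one footnote and the matching derivation code, with no new data. It is best done before unblinding, so that the handling of these subjects is not chosen with results in view.

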- If a subject has a non-zero asexual *P. vivax* parasite count at baseline, and prior to Study Day 8 has two negative counts with at least 6 hours between the counts and no positive parasite counts within this time period, parasite clearance time will be defined as the time elapsed between the first dose of study medication (including CQ) and the first of these negative counts (measured in hours).
- Subjects with a negative parasite count at baseline will be censored with a parasite clearance time of 0 hours. All other subjects will be censored at the time of the last non-missing assessment prior to Study Day 8.

Fever (FCT)

- Defined as: time from first dose of treatment to the time when body temperature falls to normal within Study Days 1-4 and remains normal for at least 48 hours up to the Day 8 visit.
- Any subject who does not have a temperature in excess of 37.4°C at any point prior to the first dose of study medication (including CQ) on Study Day 1 will be censored with a fever clearance time of 0 hours. Subjects will also be censored at time 0 if the method of temperature measurement is not consistent throughout Study Days 1 to 4 (i.e., method is not consistently oral, tympanic, or axillary).

Clearance time

- Fever clearance is considered to have been achieved once an initial temperature of $>37.4^{\circ}\text{C}$ is reduced to a value $\leq 37.4^{\circ}\text{C}$, in the absence of value $>37.4^{\circ}\text{C}$ in the following 48 hours up to the Day 8 visit.
- Subjects who do not demonstrate this endpoint prior to or on the final assessment of Study Day 4 will be censored at that time point.
- As temperature is only collected twice a day whilst subjects are in the hospital, they may not have assessments for the 48 hours following an initial temperature if this occurs after they have been discharged. Clearance will be defined based on observed data only.

Gametocyte (GCT)

- Defined as: time from first dose until the first slide that was gametocyte negative and remained so at the next slide reading.
- Any subject with negative *P. vivax* gametocytes at baseline will be censored with a time to gametocyte clearance of 0 days.
- For all other subjects, gametocyte clearance will be considered to have been achieved once a negative gametocyte value has been seen, unless the next gametocyte count is positive. Time to clearance will then be defined as (time to first negative value) – (time of first dose of study medication including CQ).
- Subjects who fail to reach this endpoint will be censored at the visit of their final gametocyte assessment.

Gametocyte emergence

- Gametocyte emergence is defined as the presence of *P. vivax* gametocytes at a post-baseline visit, where the subject did not have gametocytes at baseline.

Early Failure

- An early failure is defined as a subject who either:
 - Did not demonstrate initial clearance of *P. vivax* parasitaemia (i.e. did not have two negative asexual *P. vivax* parasite counts, with at least 6 hours between the counts, and no positive counts in the interval), OR
 - Demonstrates initial clearance and has a subsequent non-zero asexual *P. vivax* parasite count on or before Study Day 32.

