3.2. Study Design

- Study TAF116564 is a prospective, double-blind, double-dummy, multicenter, comparative study.
- A total of 300 subjects will be randomized 2:1 to receive TQ/CQ or the active comparator PQ/CQ. All subjects will receive CQ on Days 1 to 3 followed by TQ or PQ and matching placebo beginning on Day 1 or 2. Tafenoquine, or matching placebo, will be given as a single, 300mg dose. Subjects will receive PQ (15mg once daily) or matching placebo for 14 days.
- The duration of the study is 180 days, including screening and randomization to treatment (Day 1), three in-hospital days (Days 1-3), four out-patient visits while on treatment with study medication (Days 5, 8, 11 and 15) and seven follow-up visits (Days 22, 29, 60, 90, 120, 150 and 180).
- Subjects must have a blood smear that is positive for *P. vivax* at entry. Blood smears will be taken for parasitological assessment twice a day for the first 3 days of the study, or until two consecutive thick blood smears are negative for *P. vivax*. Additional parasitological assessments will be conducted throughout the treatment and follow-up periods.
- Subjects are required to remain in the hospital for the first three days of the study, in order to ensure clinical improvement, to monitor early study medication compliance, and so that parasitological assessments can readily be taken twice a day. Subjects may need to remain in the hospital longer than 3 days if two consecutive thick blood smears negative for *P. vivax* are not obtained within the 3 day timeframe.
- At the Day 1 visit subjects will be screened for G6PD deficiency by a quantitative assay and the result will be determined as a percentage of the predetermined median enzyme activity of the site. Female subjects must have a minimum G6PD assay value of 40% to be enrolled, and male subjects must have a minimum G6PD assay value of 70% to be enrolled. In addition, a minimum of 50 female subjects must be enrolled that display $\geq 40\%$ - $< 70\%$ of the site median G6PD enzyme activity.
- The status of methemoglobin, an oxidized and inactive form of hemoglobin, will be assessed at selected visits.
- An independent data monitoring committee will be established to monitor, in an unblinded manner, safety in general and females with moderate G6PD deficiency in particular. The latter will ensure the frequency and severity of any hemoglobin declines in females remains as expected and remains clinically acceptable.

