- q The pharmacogenetics sample must be collected at the earliest opportunity after randomization and during the in-clinic treatment visit (Days 1-3).
- r Serum or urine pregnancy test that is routinely used at site with a test sensitivity for hCG level ≤ 25 mIU/mL. FSH serum test only for post-menopausal females with less than 6 months spontaneous amenorrhea.
- s Refer to Section 6.5 of the protocol for details on health outcome data collection.
- t Health outcomes assessments will only be collected at these visits from subjects with confirmed parasitemia or from subjects with clinically relevant hemolysis.
- u Day 2 and Day 3 PK samples must be taken 6-12 hours and 24-48 hours post TQ dose.
- v Treatment with blinded study medication will begin on either Day 1 or Day 2.

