6.1. Critical Baseline Assessments

Written, dated informed consent must be obtained from each potentially eligible subject (or his/her legal representative) by study site personnel **prior** to the initiation of any screening procedures.

Clinical and laboratory assessments will be conducted at screening (**prior to first dose of the study medication**) as detailed in the Time and Events ([Table 2](#)).

- Demographic data will be collected to include details of date of birth, gender, race and ethnicity
- Medical history will be collected

- A physical examination will be conducted including:
 - Cardiovascular examination
 - Abdominal examination including assessment of splenomegaly
 - Respiratory examination

- Vital signs will be assessed. These include height, weight, temperature (oral, axillary or tympanic), heart rate, respiratory rate, systolic and diastolic blood pressure

- Investigators will assess *P. vivax* malaria symptoms at baseline. The incidence and severity (defined as absent, mild, moderate, severe, or unknown) of the following symptoms will be recorded: chills and rigours, headache, dizziness, abdominal pain, anorexia, nausea, vomiting, diarrhea, pruritis or itching, and coughing. The date of onset of symptoms will also be recorded. The investigator or designee can also assess and record any other *P. vivax* malaria symptoms.

- Blood smears for parasitological assessment will be collected and examined for asexual parasite count and gametocyte blood count (see Section [6.3](#) and the SPM for further details).

- A blood sample will be collected on a filter paper and stored for future plasmodium genotyping analysis. An additional blood sample will be collected to conduct exploratory plasmodium whole genome sequencing.

- Current and prior medications will be reviewed including any anti-malarial medication that has been used.

- G6PD status will be assessed using quantitative spectrophotometric analysis (further instructions can be found in the SPM). The quantitative analysis will

be used to determine the subject's eligibility for the study. One or more G6PD rapid point of care tests may also be performed at baseline.

- Periodic external quality assurance testing will be performed to ensure high quality G6PD assay data. Procedures for quality assurance will be described in detail in the SPM.
- A blood sample will be collected on Day 2 for G6PD and CYP2D6 genotyping.
- Laboratory Assessments:

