6.4. Safety

The timing and details of all safety assessments are provided in the Time and Events table in Section 6. Additional details on specific assessments are provided below. Blinded safety information will be reviewed on a monthly basis by a GSK/MMV safety review team.

There are two co-primary safety endpoints in this study: clinically relevant hemolysis will be compared between the two treatment groups in all subjects, and in 50 female subjects with moderate G6PD deficiency ($\geq 40\%$ to $< 70\%$ of the median site value).

Information on concomitant medication will be collected daily while the subject is an in-patient, at all scheduled treatment and follow-up visits, and if there is a relapse or premature withdrawal visit.

Physical examinations will be performed daily during in-patient days, on each scheduled treatment and follow-up visit at Days 8, 15, 22, 29, 60, 90, 120, 150 and 180 and if there is a relapse or premature withdrawal visit.

Vital signs will be performed twice daily whilst an in-patient and on follow-up visits at Days 8, 11, 15, 22, 29, 60, 90, 120, 150 and 180 and if there is a relapse or premature withdrawal visit.

12-lead ECG will be performed at screening, 12 hours (± 30 minutes) after the first dose of blinded study medication, and at Day 29. ECG assessments will also be conducted in cases of relapse or early withdrawal. ECGs will be performed in triplicate at screening but single ECGs will be performed subsequently as indicated in [Table 2](#) unless prolonged QTc is seen.

Clinical chemistry and hematology samples will be analyzed by local laboratories. Evaluations will be made at screening, treatment Days 3, 5, 8, 11, 15 and follow-up Days 22, 29, 60, 90, and 120. These assessments will also be performed if there is a relapse or withdrawal visit. The panel of tests to be analyzed are detailed below in [Table 3](#) and [Table 4](#). All laboratory data will be used for the purpose of safety analysis and reporting for this study. Any laboratory tests the attending physician or investigator deems necessary for the care and safety monitoring of the study subjects will be conducted by the local laboratory. All laboratory results that are considered clinically significant should be recorded as AEs.

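### Fever clearance time is censored at 0 h for any change of thermometer method on Study Days 1–4, which discards clearances already observed before the change

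*Supplement*

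**What the plan says.** The rule is in the fever part of the clearance-time derivations, RAP Amendment 1, section 13.6.4: "Subjects will also be censored at time 0 if the method of temperature measurement is not consistent throughout Study Days 1 to 4". Clearance itself requires a pre-dose temperature above 37.4°C, a fall to 37.4°C or below within Study Days 1–4, and no higher value in the next 48 hours, up to the Day 8 visit. The same 37.4°C limit applies whichever method is used.

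Other places that bear on it:

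- Protocol Amendment 5, section 6.1, allows oral, axillary or tympanic readings and does not ask for one method within a subject.
- Protocol Table 2, footnote g: "Vital signs are to be performed twice a day on Days 1 through 3, at least 4 hours apart". Section 6.4 adds: "Vital signs will be performed twice daily whilst an in-patient".
- The protocol's own FCT definition (section 8.3.4.3) has no condition on method, and RAP section 2.1 does not list the condition among its changes from the protocol.
- RAP section 8.1.2 analyses FCT in the mITT population by Kaplan-Meier and by a Cox model with region and treatment. The table shows the number censored, without reasons.
- RAP section 13.7.2.3 says that mITT subjects will not be left out of any statistical analysis.

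**The concern.** Censoring at 0 h sounds like a way of handling incomplete data, but it gives the subject no follow-up at all. One reading by another method within the four days is enough, including a reading taken after the fever had already cleared. Two things follow. Events that were properly observed are thrown away. And whether a subject enters the analysis is decided partly by what happens after the event, which a time-to-event analysis should avoid.

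FCT is a named secondary endpoint. At stake are the number of events and the precision behind the quartiles and hazard ratio. The reader also cannot see the loss, because the censored count merges subjects without fever at baseline, subjects with mixed methods and subjects who did not clear.

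**Working it through.** The plan gives no figure for FCT, neither a rate of mixed methods nor an expected loss, so there is nothing to reproduce. Three checks follow.

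**1. Is censoring at 0 h the same as deletion?** In 200 simulated subjects, 20% flagged at random were either censored at 0 h or removed. The Kaplan-Meier curve was identical (median 16.04 h both ways), and so were the Cox log hazard ratio (0.0826) and its standard error (0.1656). The rule is deletion from this analysis. Such a subject is still counted as censored, but contributes nothing, which in effect conflicts with section 13.7.2.3.

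**2. Does it discard observed events?** Take a subject febrile by the oral route before dosing. The first normal oral reading is on the evening of Day 1, and all oral readings stay normal through the evening of Day 3, 48 hours later. One axillary reading on Day 4 turns this event into a time of 0 h. Since dosing starts on Day 1, a full 48-hour confirmation cannot end before Day 3. Complete events are therefore lost only through switches from Day 3 onward. A switch on Day 1 or 2 loses partial follow-up instead.

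**3. How many subjects might be lost?** Inputs: two readings a day on Days 1–3 give 2 × 3 = 6; a subject still admitted on Day 4 has 2 more, so 8. The chance q that a reading uses another method is an assumption, taken as independent between readings. Two formulas bracket the answer:

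- A: the first reading sets the method, so loss = 1 − (1 − q)^(n−1).
- B: any reading may be the odd one, so loss = 1 − (1 − q)^n − q^n.

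| q | A, n = 6 | B, n = 6 | A, n = 8 | B, n = 8 |
|---|---|---|---|---|
| 1% | 4.9% | 5.9% | 6.8% | 7.7% |
| 5% | 22.6% | 26.5% | 30.2% | 33.7% |

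Example for A: 1 − 0.99^5 = 0.049. The Meta-Analysis Plan, section 3, gives 251 randomised. If all of them were febrile at dosing (an upper limit) with six readings, formula B gives 251 × 0.0585 ≈ 15 lost at 1% and 251 × 0.2649 ≈ 67 at 5%.

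**Does a longer stay matter?** Protocol section 3.2 says: "Subjects may need to remain in the hospital longer than 3 days if two consecutive thick blood smears negative for" the parasite are not obtained in that time. Under B, for q from 0.5% to 10%, the ratio of loss for 8 versus 6 readings runs from 1.33 down to 1.22. For 8 versus 7 readings it runs from 1.14 to 1.09. A simulation assumed that 10% or 20% of subjects clear slowly (median 48 h versus 18 h) and have 8 readings while the rest have 6. With q from 1% to 10%, the rule lowered the median FCT by 0.0 to 0.7 h.

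**The case against.** A reader might infer that the rule preferentially removes slow parasite clearers and so tilts FCT toward quick clearance, perhaps differently by arm. The documents do not support that. It needs switches to fall at random on individual readings; if they follow site or device, or occur on Days 1–3, a longer stay adds nothing. The window closes at Day 4, so a longer stay adds about two readings at most. Subjects who clear quickly can have Day 4 readings too, because vital signs accompany the pharmacokinetic draws and Protocol Table 2, footnote u, says: "Day 2 and Day 3 PK samples must be taken 6-12 hours and 24-48 hours post TQ dose". A tilt in FCT also needs parasite and fever clearance to be correlated, which is not shown. A difference between arms needs removal to differ by arm, and this is a double-blind, double-dummy trial with the same chloroquine in both arms.

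Nor is all of the subject's data lost. RAP section 8.2.3 keeps temperatures in the vital-sign summaries whatever the method, and they are listed.

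The rule also has a reason. With one 37.4°C limit for three methods, a switch could create or hide a crossing. The Study Procedures Manual, which is not shown, may fix one method per subject. FCT is one of many secondary endpoints, no hypotheses are tested, and its table is not a headline display.

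All of this stands, and it makes the point modest. It does not justify discarding a clearance completed by one method before any switch.

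**Conclusion.** The rule removes subjects from the FCT analysis on the strength of readings that may come after the event, and it loses observed clearances. That follows from the text and needs no assumption. The size is unknown: about 5–6% lost at an assumed 1% switch rate per reading with six readings, about 23–27% at 5%, and none if sites kept to one method. Somewhat greater removal of subjects with longer stays is possible but not shown, and no bias in the comparison of tafenoquine with primaquine is shown. The consequence is lost information and a loss that is not reported by reason.

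**What to change.** Replace the sentence in RAP section 13.6.4 with these rules:

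1. Derive FCT from the readings up to the first change of method.
2. Count clearance as an event if the fall to 37.4°C or below and its 48-hour confirmation, judged on the readings available, both precede the change.
3. Otherwise censor at the last same-method reading before the change. Use 0 h only when no post-dose reading shares the pre-dose method.
4. Report by arm the number censored for mixed method, and keep the present time-0 rule as a sensitivity analysis.

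This keeps the single-method principle. It also resembles the approach in the same section for anti-malarial co-medication, where time to relapse is censored at the last negative assessment beforehand and at 0 only as a fallback. It is preferable to filtering out off-method readings over the whole period. The RAP notes: "As temperature is only collected twice a day whilst subjects are in the hospital", and it judges clearance on observed data only, so dropping readings could make clearance easier to declare.

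The cost is a few lines of RAP text, slightly more derivation work and one extra table. Some subjects will still be censored early, and where the pre-dose reading is the odd one nothing is recovered.
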